8.4. Data sources

8.4.1. Data recorded by the physician:

Upon inclusion

The inclusion visit enables the physicians to document the following parameters:

- Compliance with inclusion criteria;
- ECOG performance status;
- Patient's sociodemographic characteristics;
- History of the disease;
- Biological, histological and metastatic examination data;
- Conditions of sunitinib use;
- Concomitant treatments;
- Issuing of treatment support equipment and planned support.

During the end-of-cycle 1, 2 and 4 visits

During the follow-up visits, the following parameters are recorded by the physicians, via the e-CRF:

- Disease progression;
- Biological, histological and metastatic examination data;
- Possible modifications to the conditions of sunitinib use (change of dose, treatment plan, temporary interruption or termination);
- Concomitant treatments;
- Pharmacovigilance data (recording of adverse events, degree of severity and description of the AE: intensity, symptoms, impact on patient follow-up, examinations performed, actions implemented);
- History of calls and consultations with a healthcare professional during the cycle (scheduled and unscheduled).
- Hospitalisation during the cycle (scheduled and unscheduled).
- Issuing of treatment support equipment and planned support.

The end of cycle 4 visit will represent the final visit.

At the end of the study

The participating physicians will fill in on the e-CRF a questionnaire on their level of satisfaction concerning the call platform.

8.4.2. Data recorded via the call centre:

The patients will have received phone calls on W1, W2, W3, W4 and W5 of the first two cycles, then every two weeks, W2 and W4 for cycles 3 and 4.

During the calls made by the nurses, all of the data of the specific call questionnaires (Appendix 6: Nurse intervention script) shall be recorded via a CATI system used to instantaneously enter the data collected into a software application.

The following data will be collected:

- Number of call attempts
- Patient's general condition;
- Treatment taking;
- Tolerance and occurrence of adverse events (description of the AE: intensity, symptoms, impact on the patient, examinations performed, actions implemented;
- Proposed action

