(auto)	--/--	 Non-serious  Serious If serious, severity criteria (several possible answers):  Caused death If death, specify: Date of death: --/---/--- (DD/MM/YYYY) Cause of death: _____  Life-threatening  Hospitalization / prolonged hospitalization  Anomaly / congenital malformation  Permanent or major invalidity or disability  Medically significant event	 Grade 1  Grade 2  Grade 3  Grade 4  Grade 5	 Does not affect daily life  Makes certain actions difficult to accomplish  Affect activities of daily life	 Related to taking Sutent®  Related to a concomitant medicine If other, specify the treatment _____	 Recovered If recovered, recovery date: --/--/-- (DD/MM/YY YY)  Recovered with sequelae If recovered, recovery date: --/--/-- (DD/MM/YY YY)  Recovering  Not recovered  Unknown	 Prescription of a treatment, specify:  Medical consultation (general practitioner, specialist, emergency department) →§3.7  Hospitalisation. →§3.7  Other, specify:  Not applicable	 Interruption (temporary, permanent, or delayed) If causality = Sutent®, →§3.5  Dose reduction If causality = Sutent®, →§3.5  Dose increase If causality = Sutent®, →§3.5  Dose unchanged  Unknown  Not applicable
---------	-------	-------	--	--	---	--	---	--	---

(Dynamic table: auto-incrementation of the number of rows displayed according to the number of AEs declared above. The

table is shared with that of AEs declared by the nurses using the CATI system).

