3.7 Scheduled and unscheduled medical procedures

History of calls to a healthcare professional during the previous cycle

Has the patient contacted a healthcare professional since the last documented visit dated [date of last recorded visit], excluding any cases of adverse event? Yes No

If yes, please fill in the following table for each new call to a healthcare professional:

Date	Type of call	Specialist field of the healthcare professional	Reason for the call	Action implemented
____ / ____ / _____ (DD/MM/YYYY)	 Scheduled  Unscheduled	List {General practitioner; Oncologist; Cardiologist; Nephrologist; Accident and Emergency; Nurse; Other, etc.}	 AE*; If yes, specify which one:  Other, specify: _____	 Temporary Sutent® interruption  Treatment prescribed Specify: _____  Consultation with medical specialist  Nephrologist  Cardiologist  Other: _____  Consultation with attending physician  Emergency department. Date: _____ Location: _____ Hospitalisation:  Yes  No  Hospitalisation. Date: _____ Location: _____  Hygiene and nutrition advice  Other, specify: _____  Not applicable

(Dynamic table: rows can be added if more than two consultations are observed)

*: If AE ticked, the physician has already described this AE in the previous section, the e-CRF will thus display the list of AEs already filled in and the physician can simply select the relevant AE (without having to describe it again)

History of consultations with a healthcare professional during the previous cycle

Has the patient consulted a healthcare professional since the last documented visit dated [date of last recorded visit], excluding any cases of adverse event? Yes No

If yes, please fill in the following table for each new consultation with a healthcare professional:

Date	Type of consultation	Specialist field of the healthcare professional	Reason for consultation	Action implemented

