____ / ____ / _____ (DD/MM/YYYY)	 Scheduled  Unscheduled	List {General practitioner; Oncologist; Cardiologist; Nephrologist; Accident and Emergency; Nurse; Other, etc.}	 AE*. If yes, specify which one:  Other, specify: _____	 Sutent® dose modification  Temporary Sutent® interruption  Termination of Sutent®  Treatment prescribed Specify: _____  Consultation with medical specialist  Nephrologist  Cardiologist  Other: _____  Consultation with attending physician  Emergency department. Date: _____ Location: _____ Hospitalisation:  Yes  No  Hospitalisation. Date: _____ Location: _____  Hygiene and nutrition advice  Other, specify: _____  Not applicable

(Dynamic table: rows can be added if more than two consultations are observed)

**: If AE ticked, the physician has already described this AE in the previous section, the e-CRF will thus display the list of AEs already filled in and the physician can simply select the relevant AE (without having to describe it again)*

History of hospitalisations during the previous cycle

Has the patient been hospitalised since the last documented visit dated [date of last recorded visit], excluding any cases of adverse event?

Yes No

If yes, please fill in the following table for each new hospitalisation:

Date	Type of hospitalisation	Duration	Location	Reason	Action implemented

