Overview of advice and preventive actions covered	X	X	X
Declaration + transmission of report sheets	X	X	X

* During ad hoc calls to the freephone number, the nurse can go directly to the desired section of the questionnaire in order to meet the patient's request

C. PRE-CALL CHECK-LIST

Instruction: Check-list pre-filled for the nurse. This sheet can be printed from the CATI system at the start of the call.

The data are obtained from the physician CRF and from previous calls. The information will also be displayed during the call in the appropriate sections, where they can be updated.

[Date - time of sheet generation]

Patient characteristics		Physician information						
Name: _____ First name: _____ Age: _____		Name: _____						
ECOG: _____ (date) Heng criterion: _____ (date)		First name: _____						
Call: Week x, Cycle x (N th scheduled call)		Tel.: _____						
Information received by the patient: Verbal information from the oncologist; verbal information from the medical team; written information (specify medium)								
Medical history and current co-morbidities Diabetes; Hypothyroidism; Hyperthyroidism; Stroke; Hypertension; Deep vein thrombosis; Myocardial infarction; Angina pectoris; Kidney failure; Liver failure; Other: _____								
Concomitant treatments								
Surname	Indication	Date first taken	Status					
---	---	---	---					
Reason for prescription	Dosing	Recommendations						
---	---	---						
Adverse events (resolved and unresolved)								
AE type	AE description	Start date	Severity	Grade	Causal relationship	Change	Corrective medical action	Action on suspected treatment
Overview of all previous AEs (e-CRF + CATI) and follow-ups								
---	---	---	---	---	---	---	---	---
History of calls to a healthcare professional (scheduled and unscheduled)								
Date	Type of call	Specialist field of the healthcare professional			Reason for the call	Action implemented		
___/___/___	---	---			---	---		
History of consultations with a healthcare professional (scheduled and unscheduled)								
Date	Type of consultation	Specialist field of the healthcare professional			Reason for consultation	Action implemented		
___/___/___	---	---			---	---		
History of hospitalisations (scheduled and unscheduled)								
Date	Type of hospitalisation		Duration	Location		Reason	Action implemented	
___/___/___	---		---	---		---	---	
Nurse's comments:								
General CATI comment: _____								
Name (date): _____								

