Instruction: A summary note will be generated automatically and sent to the physician via the e-CRF. It shall comprise:

- A box with the salient points to be taken into consideration by the physician
- The phone call details (automatic: number of attempts, date and duration of the call)
- A summary of events declared by the patient (new or follow-up)
- Actions undertaken by the patient and actions recommended to the patient.
- Main advice given to the patient

Validation of any discrepancies between patient and e-CRF data will be requested.

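### SAP Tables 37 and 38 report unscheduled procedures per cycle, but the V3 column covers cycles 3 and 4 together, so a constant rate would read as a late rise

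*Protocol*

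**What the plan says.** **Endpoint and source.** Protocol 7.3.2 and SAP 6.2 define the endpoint as the mean numbers of unscheduled consultations and unscheduled hospitalisations, irrespective of any link to sunitinib. Protocol 7.3.2 bases the secondary outcomes on what physicians enter in the e-CRF (and on patient questionnaires). SAP 8.2.5.2 counts procedures reported at each follow-up visit.

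**Timing.** Protocol 8.2 places follow-up visits at about W6, W12 and W24, at the end of cycles 1, 2 and 4, with 6-week cycles. There is no visit at the end of cycle 3. The SAP calls these visits V1, V2 and V3 (V2, V3 and V4 in Protocol 8.3.1); SAP numbering is used here.

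**Look-back.** The CRF 3.7 questions (Protocol Appendix 6) run from the previous recorded visit: "Has the patient consulted a healthcare professional since the last documented visit dated [date of last recorded visit], excluding any cases of adverse event" and "Has the patient been hospitalised since the last documented visit dated [date of last recorded visit], excluding any cases of adverse event". The heading above the second is "History of hospitalisations during the previous cycle", and Protocol 8.4.1 lists "Hospitalisation during the cycle (scheduled and unscheduled").

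**Presentation.** SAP 8.2.5.2 asks for counts per cycle and per patient at each follow-up time and overall. Table 37 (proportions with at least one procedure) is titled by cycle and Table 38 (counts) per cycle. Both have columns V1, V2, V3 and an overall Call Center column with no stated denominator.

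**Adverse-event procedures.** In the CRF 3.4 adverse event table, one corrective-action box reads "Medical consultation (general practitioner, specialist, emergency department) →§3.7". The hospitalisation box carries the same pointer. The CRF 3.7 tables offer an adverse event as a reason, and SAP 8.2.3 plans to describe the reason as adverse event or other.

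**The concern.** Columns described in the same unit should cover the same exposure. V1 and V2 each hold one cycle; V3 holds up to two. A reader comparing them would see visits and admissions rise late in follow-up, just when calls drop from five per cycle to two, and could link the two. Nothing need have changed for that pattern to appear. The unlabelled overall column adds to the problem, because it could be a total, a rate per cycle or an average of the three visit columns.

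The secondary worry is completeness. Protocol 6.1.3 suggests that the platform could reduce unscheduled visits caused by poor tolerance. A physician who reads the CRF 3.7 questions literally would leave out exactly those visits.

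**Working it through.** **Step 1. Reproduce the visit schedule.** Inputs from Protocol 8.2: 6-week cycles, visits at the end of cycles 1, 2 and 4. Visit week = 6 × cycle number = 6, 12, 24, which matches the protocol. Look-back windows are 6 − 0 = 6, 12 − 6 = 6 and 24 − 12 = 12 weeks, that is 1, 1 and 2 cycles.

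**Step 2. Mean counts (Table 38).** Let r be a constant rate per cycle. Let s be the share of patients in cycle 3 who complete cycle 4; assume the others contribute cycle 3 only. Expected V3 mean = r(1 + s). The documents give neither r nor s, so both are assumptions; r = 0.20 is for illustration.

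| s | V3 in units of r | V1 / V2 / V3 at r = 0.20 |
|---|---|---|
| 100% | 2.0 | 0.20 / 0.20 / 0.40 |
| 80% | 1.8 | 0.20 / 0.20 / 0.36 |
| 60% | 1.6 | 0.20 / 0.20 / 0.32 |
| 40% | 1.4 | 0.20 / 0.20 / 0.28 |

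**Step 3. Proportions with at least one procedure (Table 37).** Assuming Poisson counts and s = 100%, a one-cycle window gives 1 − exp(−r) and V3 gives 1 − exp(−2r).

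| r | V1 and V2 | V3 |
|---|---|---|
| 0.10 | 9.5% | 18.1% |
| 0.20 | 18.1% | 33.0% |
| 0.50 | 39.3% | 63.2% |

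**Step 4. Overall column.** At r = 0.20 with no stopping, the total is 4 × 0.20 = 0.80 per patient, or 0.80 / 4 = 0.20 per cycle started. A plain average of the three visit columns is (0.20 + 0.20 + 0.40) / 3 = 0.27, which is 1.33r. If 20% stop at the end of each cycle (assumed), cycles started per patient are 1 + 0.8 + 0.64 + 0.512 = 2.952. The total is then 2.952 × 0.20 = 0.59, and still 0.20 per cycle started. The meaning of the column has to be stated.

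**Step 5. Can entries be allocated to cycles?** CRF 3.7 rows are dated. CRF 3.8 records day 1 of the next cycle, which gives the starts of cycles 2 and 3. For cycle 4, the follow-up form (CRF section 3) records a scheduled cycle end date at every visit including W24, and the nurse script (Appendix 7, D.2.2.1) asks for the restart date. SAP Table 8 already plans the duration of each of the four cycles, and Tables 32 and 34 show dose reductions and interruptions in four separate cycle columns. Cycle boundaries are therefore needed anyway.

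**Step 6. The adverse-event wording.** The questions exclude adverse-event cases, yet the tables behind them accept an adverse event as a reason and the adverse event form points to them. Nothing states which prevails. If a is the share of procedures driven by adverse events and g the share of those lost, the count retained is 1 − a × g. With a assumed between 20% and 80% and g between 0 and 1, that runs from 100% down to 20%. This range is too wide to be a useful bound, so the loss is not sized.

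**The case against.** **The unit may already be a rate.** SAP 8.2.5.2 speaks of numbers per cycle and per patient, and cycles per patient are derived under SAP 8.2.1. One could read this as already divided by cycles covered. But no divisor is stated for V3, and the proportions in Table 37 cannot be repaired by division. What stands is that one sentence would settle the counts.

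**The gap is visible.** The columns are headed end of cycle 2 and end of cycle 4, so a careful reader can see that a cycle is skipped. That is true, but the table titles still say by cycle or per cycle.

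**V3 might hold cycle 4 only.** The CRF 3.7 heading and Protocol 8.4.1 refer to a single cycle, so a reader might infer that cycle 3 is missed altogether. The questions themselves carry the date of the last recorded visit, so the documents do not support assuming this.

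**The adverse-event exclusion may only prevent double entry.** With the pointer from CRF 3.4, the adverse-event reason box and a footnote letting the physician pick an event already entered, the exclusion can be read as meaning beyond those already routed here. That is plausible. Partial cross-checks also exist: CRF 3.4 says its "table is shared with that of AEs declared by the nurses using the CATI system", and Appendix 7 adds: "Validation of any discrepancies between patient and e-CRF data will be requested". The wording still conflicts, but loss of data is a possibility, not a demonstrated fact.

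**Conclusion.** The timing point holds. As specified, V3 covers up to two cycles and sits under a per-cycle title beside two one-cycle columns. With a constant rate it reads up to 2r. The full doubling requires every patient in cycle 3 to complete cycle 4; with 40% to 80% completing, V3 reads 1.4r to 1.8r. It would be wrong to say that V3 is always double. Table 37 has the same unequal windows.

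The adverse-event wording is a secondary point about completeness, of unknown size and possibly zero. Three stronger readings are tempting but not supported:

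- A reader might infer that the SAP lacks a rule for merging physician and nurse (CATI) records. Protocol 7.3.2 and SAP 8.2.5.2 already name the source: physician e-CRF entries declared at visits. No merging rule is missing.
- A reader might infer that adverse-event procedures are excluded from the endpoint. The CRF 3.4 routing and the reason box in CRF 3.7 show that they are expected there. The similar question about calls does not bear on the endpoint, which counts consultations and hospitalisations only.
- As extracted, Table 38 shows no row labelled unplanned for hospitalisations or for the combined counts, so a reader might infer that these will not be reported. SAP 8.2.5.2 requires them, and the missing label may come from PDF reading or translation.

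SAP 4.1 rules out statistical tests and SAP 8.1.1 makes the analysis purely descriptive, so no inference is affected. The harm is a misleading table for one secondary endpoint. Priority is modest.

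**What to change.** In the SAP or its derivation specification, before the tables are produced:

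1. Allocate dated CRF 3.7 entries to cycles 1 to 4 with the cycle dates used for Table 8, and name the source of those dates. The scheduled cycle end date on the W24 form helps for cycle 4. Alternatively, for the counts, divide by the cycles each patient covered. Where neither is possible, label V3 as cycles 3-4 and do not call it per cycle. In Table 37, use cycle columns or the cycles 3-4 label, since division does not apply to proportions.
2. Give the overall column as a total per patient and as a rate per cycle started.
3. Keep CRF 3.7 as the source and do not add CATI entries to the main count. List adverse event rows marked consultation or hospitalisation that have no matching CRF 3.7 entry, and query them or report their number as a completeness check. The freeze was scheduled for January 2019 and the SAP is dated 06/02/2019, so reporting may be the only option left.
4. When producing Table 38, make sure that unplanned hospitalisations and unplanned combined counts appear, as SAP 8.2.5.2 requires.

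The cost is one derivation rule, one listing and some labels, all from data already collected. No CRF change is needed. Protocol 8.7.4 asks that changes to statistical methods be documented in the report, so a short note there completes it.

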3.8 Decision concerning sunitinib treatment

Participating physician's decision following this follow-up visit

Continue treatment, date of day 1 of next cycle: ____ / ____ / ____ (DD/MM/YYYY)

Dose and dosage regimen:

50 mg/day, 4 weeks followed by a 2-week break

Other, specify: _____

Termination of current treatment, date stopped: ____ / ____ / ____ (DD/MM/YYYY)

Break from therapy

Change of line of therapy (fill in the end of treatment appraisal form)

Continued break from therapy

Resumed sunitinib treatment, date resumed: ____ / ____ / ____ (DD/MM/YYYY)

In the event of treatment termination, the physician is directed to the end of treatment form.

3.9 Sunitinib treatment accompanying measures if treatment continued

The patient was given information for his/her Sunitinib® treatment since the last documented visit dated [date of last recorded visit] (several boxes possible):

- no new information
- by yourself
- by the care team. Specify the type of individuals involved (nurse, intern, etc.)

by means of an information leaflet or any other medium / material / document issued to the patient:

Specify the medium: _____

other: _____

4 END-OF-TREATMENT FORM

DATA CONCERNING TERMINATION OF THE FIRST LINE OF TREATMENT

Date treatment stopped / / (DD / MM / YYYY)

Reason for termination of Sutent®

- Disease progression
 Toxicity, specify _____

has an AE report form been filled in: Yes No

if no, please report the AE

- Intercurrent disease, specify _____
 Patient's choice _____
 Physician's choice, specify _____
 Death _____

has an AE report form been filled in: Yes No

if no, please report the AE

- Other, give details: _____

DISEASE OUTCOME

Best response to first line treatment with sunitinib (RECIST criteria)

- Complete response Stable disease
 Partial response Disease progression
 Not assessable If NA, Reason: _____

Date of first progression before initiation of a second metastatic line (if not specified in previous tumour evaluation)

 / / (DD / MM / YYYY)

14.7. Appendix 7: Intervention by nurse

RENACALL STUDY

Evaluation of the impact of a therapy management platform on the management of patients suffering from advanced/metastatic renal cell carcinoma and receiving first line treatment with sunitinib, versus standard follow-up

INTERVENTION BY NURSE

A. MANAGEMENT BY THE THERAPY MANAGEMENT PLATFORM ¹

The patients will be monitored not only in the standard manner, but also via the therapy management platform.

Calls shall be made by nurses specially trained for this role, from a centralised platform based in the Paris region. If necessary, the nurses may be assisted by physicians from the therapy management platform.

The aim of these calls is to support the patients in the management of their treatment by listening to and advising them, implementing preventive measure and taking actions when deemed necessary; the purpose of these calls is to support patients in the management of their sunitinib treatment.

Call frequency is presented in the following figure:

[figure not shown]

Figure 1. Call frequency for patients

The chosen rate is of:

- For the first two cycles, C1 and C2: 5 calls during the first 5 weeks of each cycle (i.e. one call per week; no call during week 6 as the patients are usually seen in consultation),
- For cycles 3 and 4: 2 calls per cycle on weeks 2 and 4.

These calls will be made for patients treated with Sutent®; in the event of termination of treatment during the follow-up period, the call following termination will close the intervention. In the event of cycle start postponement, the first call made shall be postponed to match the expected organisation (cycles 1 and 2: first call during week 1 of the cycle; cycles 3 and 4: first call during week 2 of the cycle).

¹ Information obtained from the RENACALL protocol

B. DATA COLLECTED

	1 st call	Follow-up calls	Freephone number call
General information concerning the interview	X		
Patient's general condition	X	X	X
Introduction: treatment initiation	X		
Introduction: support follow-up and treatment resumption		X	X
Treatment compliance (+ Morisky at W4 cycles 1, 2 and 4)	X	X	X
Initial and support prescriptions	X		
Additional prescriptions		X	X
Care pathway (medical procedures, hospitalisation, emergencies)	X	X	X
Examination and additional tests follow-up	X	X	X
Tolerance, reported side effects	X	X	X
Monitoring of side effects and corrective actions		X	X
Setting appointments	X	X	X
Overview of advice and preventive actions covered	X	X	X
Declaration + transmission of report sheets	X	X	X

* During ad hoc calls to the freephone number, the nurse can go directly to the desired section of the questionnaire in order to meet the patient's request

C. PRE-CALL CHECK-LIST

Instruction: Check-list pre-filled for the nurse. This sheet can be printed from the CATI system at the start of the call.

The data are obtained from the physician CRF and from previous calls. The information will also be displayed during the call in the appropriate sections, where they can be updated.

[Date - time of sheet generation]

Patient characteristics		Physician information						
Name: _____ First name: _____ Age: _____		Name: _____						
ECOG: _____ (date) Heng criterion: _____ (date)		First name: _____						
Call: Week x, Cycle x (N th scheduled call)		Tel.: _____						
Information received by the patient: Verbal information from the oncologist; verbal information from the medical team; written information (specify medium)								
Medical history and current co-morbidities Diabetes; Hypothyroidism; Hyperthyroidism; Stroke; Hypertension; Deep vein thrombosis; Myocardial infarction; Angina pectoris; Kidney failure; Liver failure; Other: _____								
Concomitant treatments								
Surname	Indication	Date first taken	Status					
---	---	---	---					
Reason for prescription	Dosing	Recommendations						
---	---	---						
Adverse events (resolved and unresolved)								
AE type	AE description	Start date	Severity	Grade	Causal relationship	Change	Corrective medical action	Action on suspected treatment
Overview of all previous AEs (e-CRF + CATI) and follow-ups								
---	---	---	---	---	---	---	---	---
History of calls to a healthcare professional (scheduled and unscheduled)								
Date	Type of call	Specialist field of the healthcare professional			Reason for the call	Action implemented		
___/___/___	---	---			---	---		
History of consultations with a healthcare professional (scheduled and unscheduled)								
Date	Type of consultation	Specialist field of the healthcare professional			Reason for consultation	Action implemented		
___/___/___	---	---			---	---		
History of hospitalisations (scheduled and unscheduled)								
Date	Type of hospitalisation		Duration	Location		Reason	Action implemented	
___/___/___	---		---	---		---	---	
Nurse's comments:								
General CATI comment: _____								
Name (date): _____								
Oncologist's response: _____ (where applicable)								

Name (date): _____

Oncologist's response: _____ (where applicable)

D. INTERVENTION BY NURSE

Info: Depending on the type of call (1st call, cycle-start call or last call), the nurse will be automatically directed to the relevant patient questionnaire. The important data obtained from the physician CRF and from previous CATI calls will be made available to the nurse throughout the questionnaire and can be updated and completed.

D.1. Phone contact

- 1- Hello, I am *[Nurse's Last and First names]*, a nurse with the company **PPD** . I am calling in the context of the Sutent® treatment follow-up (*therapy management platform*). Could I speak to *[Patient's Last and First names]*.
 - *If Yes*, I am calling you for your support in taking the Sutent® treatment. Are you available to talk about it?
 - *If Yes, go to "Start call"*
 - *If not, or not available at this time:* go to "Unsuccessful call / appointment"

Setting appointments

Info: The CATI Appointment module allows periods of unavailability to be specified, during which the patient does not wish to be called. The preferred call times are available via this module.

- If first call:
The first interview must be held within 7 days of prescription of your Sutent® treatment, that is between *[Sutent® prescription date]* and *[date + 7 days]*. Would you be available during this period? At what time could we call you?
↳ *[Make an appointment]*
- Subsequent calls:
In order to respect the call schedule, it was agreed that we would call you between *[theoretical call date -1 day]* and *[theoretical call date +1 day]*. Would you be available during this period? At what time could we call you?
↳ *[Make an appointment]*

D.2. Introduction and general discussion

D.2.1. General introduction to the first call:

Info: Information to present to the patient during the first call only

- ↳ A few days ago, your oncologist, Dr *[Doctor's Last and First names]* offered you regular telephone support to assist you in the management and tolerance of the Sutent® treatment he/she prescribed for you. I am a member of the team of nurses working in collaboration with your physician. (*Whenever possible, you will speak with me during your future calls*).
- ↳ I propose to call you on a regular basis to answer any questions you may have, to discuss your health and to advise you in the management of your treatment. For this, it

is agreed that i will call you once a week for the first 3 months of treatment, then once every two weeks for the following 2 cycles. (*In all, 14 calls are scheduled*)

↳ I would also like to point out that the purpose of these calls is not to replace Dr *[Doctor's Last and First names]* for the treatment or diagnosis of your disease. Your physician will continue to treat you as normal; We are here to assist you in managing your treatment, to advise you, to answer any questions you may have and to help you deal with any events that may occur. We are in constant connection with your physician, who will receive a report of each phone call and we can contact him/her by phone if necessary.

1- **If first call:** Did your physician clearly explain how to take the treatment?
Yes No

– *If yes or no: Advice on taking the treatment:* Sutent® treatment takes place in cycles: it must be taken every day (50mg once per day) for 4 weeks, followed by a 2-week break without treatment. This treatment can be taken either with or without food, with a large glass of water, at any time during the date, though preferably at a set time.

2- **If first call:** Did your physician or the medical team give you a document concerning your treatment, such as an information note or follow-up notebook? Have you read it? Yes Yes, Sutent® notebook No

– *If Yes, or Yes Notebook, Do you have any further questions?*
– *If Yes notebook! Sutent® notebook advice:* In the *notebook you were given, you can* take notes and keep a treatment calendar, along with a schedule of appointments with your physicians, or of examinations you need to do. You can also enter any adverse events or drug reactions that may occur, along with their onset date and duration. This will enable the medical and care teams to better help you manage your treatment and your health.

↳ I would ask you to have your notebook with you during the future calls so that you can readily access this information. You can also take this notebook with you during your consultations with the oncologist, in order to discuss any remarks you may have with him/her.

↳ *If Not, (check the data on the summary sheet)*

↳ *If the patient has received a document:* Your physician indicates that he/she issued you with *[document]*, do you remember? Have you read it?

3- **If first call:** Did your physician explain how you should manage any treatment-related side effects that may occur? Yes No

– *If yes or no:*

↳ Over the coming months, please do not hesitate to inform us of any problems related to your general condition that you may encounter, even the mildest ones, or that do not seem serious.

- ↳ I would also like to inform you that you can contact us on the study's freephone number *[freephone number]* should you suffer any adverse event, or should you require any other advice. You can contact us during the week between *9am and 7pm*.
- ↳ In case of a serious event, however, or for any other emergency situation, you should directly call your oncologist or the emergency services (Emergency medical services: 15 or Fire brigade: 18) who can respond rapidly and thus provide better assistance.

- 4- **If first call:** Let's go over the treatments prescribed by your physician. Has your physician prescribed any support medicines? Yes No *If yes*, Do you have the prescriptions with you? Do you know what medicines have been prescribed for you?

- *If Yes*, Do you have the prescriptions with you? Do you know what medicines have been prescribed for you?
- ↳ *[Check that the patient has the necessary information and that he/she is aware that he/she can act on his/her symptoms. Help him/her identify the treatments and their symptoms. Advise him/her to keep the prescriptions available.]*
- *If yes*, Do you have these medicines available at home?
- ↳ *[Identify the systematic prescriptions to start upon initiation of Sutent® treatment, along with the supplemental prescriptions to use as and when necessary.]*
- *If not, Check the data entered*
- ↳ *If prescriptions received*: Unless we are mistaken, the physician informed us that he/she prescribed you *[treatments]*. Do you have this prescription or treatment with you?

Table 2 + Concomitant treatments

Surname	Indication	Date first taken	Status	Reason for prescription	Dosing	Physician's advice
Overview of previous treatments						
Name : _____	 antiemetic  antidiarrhoeal  anti-neutropenic  antihypertensive  mouthwashes and local anaesthetics  emollients, moisturising creams  analgesics  anti-gastro-oesophageal reflux agents  bisphosphonates  Other, specify _____	 Date first taken: _____ / _____ / _____ (DD/MM/YYY)  when necessary	 Ongoing  Stopped, End date _____ / _____ (DD/MM/YYY Y)	 Curative  Preventive  Not available	 Dosage regimen: _____ doses _____ time(s) per day for _____ weeks  Not available	Recommendations: _____  Not available

Instruction: identifying all treatments available to the patient will allow the nurses to adapt the advice and actions to be implemented. The nurses will have received an anonymised copy of the patient's prescriptions from the physician

- 5- **If first call:** Could you tell me when you took Sutent® for the first time? Taken Not taken

- *If taken*, Date first taken: ___/___/___ (DD/MM/YYYY)
- *If not taken*, Why haven't you started the Sutent® treatment?
 - I forgot to start
 - I am stressed / anxious at the thought of taking it
 - Other, specify: _____

↳ Do you have any questions, or topics you would like to discuss before starting to take your treatment? *[Guide and advise the patient. Notify the oncologist if major problem]*

D.2.2. Introduction of the "Regular" interview (excluding the first call of the first cycle)

Info: The introduction discussion is a 'free' discussion between the nurse and the patient, to be held during each call. It concerns the patient's overall health, in order to win his/her trust at the start of the interview. These data will not be collected, unless an AE is declared.

- How have you been since our last talk? How is it going?

- ↳ *If resuming a cycle, a tumour evaluation should have been conducted during week 6*
 - Date of last tumour evaluation: ___/___/___ (DD/MM/YYYY)
 - Response: RC / RP / SD / PD / NE, reason _____
 - ↳ *If answer: encourage the patient during the conversation*
 - ↳ *If disease stable: be optimistic for the remainder of the treatment*

- Are you sleeping well?
- Do you have a good appetite?
- Are you able to maintain an activity?

- ↳ *If an AE is reported, the nurse can access the report form directly [D.5 Collecting new AEs]*

D.2.2.1. Introduction of the interview if first call of cycles 2, 3 or 4

- 1- **If start of cycle 2, 3 or 4:** Unless I am mistaken, you should have started a new Sutent® treatment cycle. Have you resumed your treatment? Yes No

- *If yes*, Date resumed: ___/___/___ (DD/MM/YYYY)
- *If No*, Why haven't you resumed the Sutent® treatment?
 - I planned to resume on: date ___/___/___ (DD/MM/YYYY)
 - I forgot to resume
 - I am stressed / anxious at the thought of resuming
 - I suffered an adverse event (see list of AEs for advice)
 - My physician delayed/temporarily interrupted my treatment

- Other, specify: _____
- ↳ Do you have any questions, or topics you would like to discuss before resuming your treatment? (Guide and advise the patient. Notify the oncologist if problem)

- 2- **If start of cycle 2, 3 or 4:** Was the dose or dosage regimen (*treatment schedule*) changed by your physician during your last follow-up visit? Yes
 No
- If no, no change, *Check the available data*
 - ↳ If a change is specified on the e-CRF [Table 1]: Your physician informed us that he/she changed [dose/regimen] for [value], did he mention this to you?
 - If Yes, (corresponds to the table below)
 - Dose changed: Yes No
 - If yes, what is the new prescribed dose: __ (mg/day)
 - Change of treatment regimen: Yes No
 - If Yes, what is the new regimen: __ every __ days for __ weeks, then __ weeks' rest.
 - Reason for change(s)?
 - AE, specify: _____
 - Other, specify: _____
 - Not available

→ In the event of an additional visit to the oncologist, the e-CRF may not have been updated. If a difference arises between physician and patient data, a validation will be requested in the call overview sent to the physician.

Table 1 - Sutent® treatment changes

Date modified:	Change of dose	If yes, new dose	Change of dosage regimen	If yes, new regimen	Reason for the modification
/ / (DD/MM/YYYY)	 Yes  No	 25  37.5  50  62.5  75  Other: __  Not available	 Yes  No	 Regimen: _____  Not available	 AE; If yes, specify which one: __  Other, specify: __  Not available

- 3- **If start of cycle 2, 3 or 4:** Let's go over the treatments prescribed by your physician. Did your physician prescribe any support medicines? Yes No
- i. If Yes, Do you have the prescriptions with you? Do you know what medicines have been prescribed for you?
 1. [Check that the patient has the necessary information and that he/she is aware that he/she can act on his/her symptoms. Help him/her identify the treatments and their symptoms. Advise him/her to keep the prescriptions available.]

ii. If yes, Do you have these medicines available at home?

1. *[Identify the systematic prescriptions to start at the beginning of the cycle, along with the supplemental prescriptions to use as and when necessary.]*

iii. If not, Check the data entered

1. *If prescriptions received:* Unless we are mistaken, the physician informed us that he/she prescribed you *[treatments]*. Do you have this prescription or treatment with you?

Table 2 + Concomitant treatments

Surname	Indication	Date first taken	Status	Reason for prescription	Dosing	Physician's advice
Overview of previous treatments						
